Online studies will follow a similar procedure, excluding the Cold Pressor Test and saliva samples (i.e., they will answer intake questionnaires and perform the learning and memory tests). Online studies may follow the two day procedure as described below, or all procedures may be done in a single session. Additionally, online participants will not be assigned to stress or control groups; we will examine how individual differences in stress (as measured via questionnaire data) influence learning and memory.

Day 1

Intake Procedures

After providing written informed consent, participants will be asked about their demographic information, medical and psychiatric conditions using self-report forms through Yale's HIPAA-aligned instantiation of Qualtrics (providing data on age, education, menstrual cycle, and significant medical history). We will also assess subjective stress, affective state, and substance use. These questions will be taken from standardized instruments such as: Alcohol Use Disorders Identification Test (Saunders, Aasland, Babor, de la Fuente, & Grant, 1993); the Positive and Negative Affect Schedule (Watson, Clark, & Tellegen, 1988); Perceived Stress Scale (Cohen, Kamarck, & Mermelstein, 1983); Difficulties in Emotion Regulation Scale (Gratz & Roemer, 2004); Trier Inventory of Chronic Stress (Petrowski et al 2020); and Life Events Checklist (Gray, Litz, Hsu & Lombardo 2004); and Menstrual Cycle Questionnaire. Participants in fMRI experiments will also complete the MRI safety screening form.

Each participant will be randomly assigned to a stress or control group. The procedures of the experiment will be identical for both sets of subjects, with the only difference being whether they experience the ice cold water or warm water arm bath (see Cold Pressor Task below). See the flowchart below for the general procedure.

Cold Pressor Test

To induce stress, we will use the Cold Pressor Test (CPT), a widely used procedure to provoke mild to moderate pain and stress in both adults and children. It has been used in many studies of autonomic reactivity, and hormonal stress responses. The CPT has been used successfully with both children and adults without reported adverse effects (Von Baeyer et al., 2005; Kowalczyk et al., 2006; Siegrist et al., 2006; Silverthorn and Michael,

Protocol Number [Protocol Number](#) Version Date and Version #

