5.5 Consent/Accent Procedures/HIPAA Authorization

Only study personnel listed in this protocol will obtain consent. During the session (upon arrival to the study site), participants will receive and sign the consent form via Yale's HIPAA-aligned instantiation of Qualtrics.

Consent forms will describe in detail the study intervention, study procedures, and risks. Written documentation of informed consent is required prior to starting any study procedures. Consent forms will be IRB-approved and the participant will be asked to read and review the document. Back-up participants will be given a separate consent form explaining the procedures and compensation.

The person obtaining consent will ensure that the potential subject is able to read and comprehend the consent. Comprehension will be assessed throughout the consent process and the participant will be given multiple opportunities to ask questions. The investigator will not enroll any participants who are determined to have limited decision-making capacity. They will have the opportunity to ask questions before and during the session. It will be stressed that any participation is voluntary and that consent can be withdrawn at any time. The conversation will take place in a private room to assure the participant's privacy. To avoid coercion, financial incentives for participation will be in line with standard subject payments. A copy of the informed consent document will be given to the participants for their records.

For online studies, participants will be presented with an online version of the consent form. They will be given as much time as they need to read the procedures, and they will indicate their consent by clicking an "I consent" button.

6 Study Methods/Procedures

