6.1 Study Procedures

Each experiment will take place across two sessions on two consecutive days. The two sessions will occur 24h apart and will each be conducted between 12-6pm to control for circadian fluctuations in cortisol levels (Lupien et al 2007). Participants will be recruited via the procedures described in 5.4.

On Day 1, participants will be greeted by a member of the study personnel and consent will be obtained. Participants will be randomly assigned to either the Stress group or the Control group. Participants will become acclimated to the study environment and complete intake questionnaires. Participants will then provide a saliva sample (#1) to determine basal levels of cortisol and alpha-amylase. Participants randomly assigned to the Stress group will then undergo the cold pressor test (arm submerged in 0-2C cold water for 3 minutes), while participants in the Control group will have their arm submerged in warm water (37-40 C) for 3 minutes. Participants in the Stress group may be informed that they will be video recorded during the task. Then, a second saliva sample (#2) will be acquired.

Participants will then undergo a brief rest period to allow for the cortisol stress response to emerge (Shields et al., 2017). The duration of this rest period may differ across experiments so that we can assess the influence on the delay between stress and learning on subsequent outcomes. Participants will sit silently or watch a neutral video during this period. If participants are enrolled in the MRI study, we may collect anatomical and resting state fMRI scans during this time.

Following this rest period, an additional saliva sample will be taken (#3), and participants will complete the behavioral learning task. Participants will be exposed to a series of displays on the computer screen (see section 4) and be asked to make responses on a computer interface. After they complete the behavioral task, they will give one more saliva sample (#4), and then be dismissed for Day 1.

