Day 2 will take place 24 hours later. Participants will again be greeted by a member of the study personnel. After giving another saliva sample (#5), they will then complete a series of memory tests. Following the test, they will give a final saliva sample (#6). The procedures of the study will then be explained to the participant, and the participant will be given the opportunity to ask questions about the study design. The participant will then be compensated for their participation.

Research staff will be responsible for implementing the interventions and collecting participant data. All study personnel will complete required human research protections training prior to the initiation of participant recruitment, and be trained on study protocols, recruitment and consenting, intervention and/or data collection procedures, and data handling and confidentiality. A Standard Operating Procedures manual will be developed to guide the conduct of the study and used in training. The PIs will supervise junior staff and provide re-training in the study protocol as needed.

Online studies will follow a similar procedure, excluding the Cold Pressor Test and saliva samples (i.e., they will answer intake questionnaires and perform the learning and memory tests). Online studies may follow the two day procedure as described above, or all procedures may be done in a single session. Additionally, online participants will not be assigned to stress or control groups; we will examine how individual differences in stress (as measured via questionnaire data) influence learning and memory.

Protocol Number [Protocol Number](#) Version Date and Version #**Visit Schedule Table**

	Recruitment (Pre-consent)	Visit 1 Day 1	Visit 2 Day 2
Review Eligibility	X		
Informed Consent		X	
Demographics		X	
Questionnaires		X	X
Saliva Samples		X	X
Behavioral Tasks		X	X
fMRI Scanning and eyetracking (if applicable)		X	
Randomization		X	
Adverse Events Reporting (if applicable)		X	X

Protocol Number [Protocol Number](#) Version Date and Version #

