6.2 Method of Assignment/Randomization (if applicable)

Participants will be pseudo-randomly assigned to the experimental groups such that the groups do not differ in age and sex. There will be no blinding procedures, as both the experimenter and participant will be aware of whether they are receiving the cold or warm water treatment.

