7.1 Sample Size Considerations

For the behavioral studies, we aim for an $N = 46$ per condition. This is consistent with the sample size of the study on which this behavioral experiment is based (Sherman & [name], 2020).

To determine the sample size for the fMRI study, we conducted power analyses based on our previous work demonstrating evidence of statistical learning in the hippocampus (Sherman et al., 2020). These results indicate that we would need $N = 40$ participants per group to detect neural effects ($d = .45$, 80% power). Thus, we will recruit 80 participants and randomly assign them to Stress ($N = 40$) or No Stress ($N = 40$) conditions.

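### Section 6.2 states neither how the age- and sex-balanced assignment is generated nor whether it is concealed, and intake-based exclusions can be made with the group already known

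*Combined protocol and SAP*

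**What the plan says.** Section 6.2 is the only place that describes the method of assignment: "Participants will be pseudo-randomly assigned to the experimental groups such that the groups do not differ in age and sex". It continues: "There will be no blinding procedures, as both the experimenter and participant will be aware" of which water condition is given.

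Three other sections call the assignment random and mention no constraint:

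- Section 4, Day 1, Intake Procedures: "Each participant will be randomly assigned to a stress or control group".
- Section 6.1: "Participants will be randomly assigned to either the Stress group or the Control group".
- Section 7.1, for the fMRI study: "we will recruit 80 participants and randomly assign them to Stress" or No Stress, 40 in each.

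On who does what, section 5.5 says "Only study personnel listed in this protocol will obtain consent", and section 6.1 says "Research staff will be responsible for implementing the interventions and collecting participant data". No section names the person or system that generates, holds or releases the sequence.

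Section 5.2 provides that a participant excluded after taking part, because of answers on an intake questionnaire, is replaced by a new recruit. Sections 6.5 and 7.7 also remove withdrawals and incomplete datasets from the analysis, and section 7.7 replaces the latter. Section 7.2.2, on subject characteristics, is marked not applicable.

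All of this concerns the in-lab studies. Online participants are not assigned to groups (sections 4 and 6.1).

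**The concern.** Every Stress versus No Stress comparison in section 7.2 relies on group membership being unrelated to who the participant is. That requires two things: nobody who decides on enrolment should know the coming assignment, and nobody who decides on exclusion should be able to act on a known one.

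The plan secures neither. Section 6.2 describes balance on age and sex as a result to be reached, not as a procedure. One way to reach it is to look at who is already in each group and steer the next person accordingly; another is a concealed stratified list made in advance. These differ greatly in how open they are to influence, and the text does not say which is meant. Separately, the intake questionnaires serve as an eligibility screen that can be applied after the group is known, by a team that is not blinded.

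If either route operated, the groups could differ at the outset in ways that the planned t-tests and repeated-measures ANOVAs would attribute to stress.

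**Working it through.** The plan states no figure on this point, so there is none to reproduce. The check has two parts.

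**1. Order of events on Day 1.**

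| Step | Section 4 | Section 6.1 |
|---|---|---|
| Consent | first | first |
| Intake questionnaires | second | third |
| Assignment | third | second |
| Water immersion | after both | after both |

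The visit table in section 6.1 puts eligibility review before consent, and questionnaires and randomization both at Visit 1. It gives the day, not the order within the day.

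Set beside section 5.2:

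- On the section 6.1 order, the group is set before the intake answers exist, so an exclusion based on those answers can be made with the group known.
- On the section 4 order, the answers exist first. But section 5.2 speaks of exclusion after participation, and by then the group is known anyway.

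Making the two sections agree is therefore not enough. The eligibility decision itself has to come before the group is revealed.

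**2. How guessable a balancing rule could be.** Since the algorithm is not given, this is an illustration under assumptions: 80 participants (section 7.1), 1:1 allocation, sex and a two-level age band each split 50/50, and a guesser who knows the rule and all past assignments. Chance is 50%.

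*Minimisation* (favour the group that is behind with probability p, toss a coin at ties). Let u be the simulated share of assignments made when one group is behind.

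Correct-guess rate = p × u + 0.5 × (1 − u)

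- p = 0.7, u = 0.835: 0.5845 + 0.0825 = 0.667
- p = 0.8, u = 0.790: 0.632 + 0.105 = 0.737
- p = 0.9, u = 0.751: 0.676 + 0.1245 = 0.800
- p = 1.0 (always the group behind), u = 0.718: 0.718 + 0.141 = 0.859

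The directly simulated rates were 67%, 74%, 80% and 86%. With 92 participants (46 per condition in section 7.1, times two) they were the same within one percentage point.

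*Permuted blocks of known size within four sex-by-age strata.* For complete blocks:

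- Blocks of 2: (1/2 + 1)/2 = 0.75. This equals always filling the smaller group within a cell, with ties at random.
- Blocks of 4: (1/2 + 2/3 + 2/3 + 1)/4 = 0.708.

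The simulation, which includes unfinished blocks, gave 74%, 70% and 67% for blocks of 2, 4 and 6. The share of assignments that were fully determined was 49%, 31% and 22%.

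Every balancing scheme tried can be guessed above chance by someone who sees the history and knows the rule. Restricted schemes of the usual kind (67% to 80%) are not much harder to guess than filling the smaller group in a cell (75%). The protection comes mainly from concealment and from the timing of the reveal. Blocks of random, undisclosed size were not simulated.

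**The case against.** The strongest reply is that this is missing detail rather than a defect. Restricted randomization is still random. Section 7.1 itself fixes 40 and 40, which simple randomization would not guarantee, so the general wording already allows a restriction. A concealed, centrally held stratified list would fit section 6.2. Consent precedes assignment in section 6.1, which narrows selective enrolment. No memory or learning test is described before assignment, so it is unclear what anyone would select on. The hypotheses also point in opposite directions (better statistical learning, worse episodic memory), so favouring generally strong or weak performers would not easily produce the predicted pattern.

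Much of this stands, and it rules out several stronger readings that a reader might infer:

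- *That unblinded staff make the assignment.* Section 6.2 says the experimenter knows the water condition. It does not say who assigns. Knowing the condition at delivery is a matter of performance and detection bias, not proof that the allocation was open beforehand.
- *That the next group can be predicted.* This depends on an algorithm the protocol does not state, and on staff knowing both it and the history.
- *That the sections contradict each other.* The descriptions differ and need reconciling, but the difference does not prove a non-random method.
- *That later analysis could never detect a problem.* The intake questionnaires and the first saliva sample precede the water immersion and could be compared by group, although section 7.2.2 plans no such comparison.
- *That a bias in standard deviations can be given.* That needs an assumed shift in performance between selected participants, which the documents do not supply.

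What the reply does not answer is the intake route. Consent before assignment does nothing about exclusions decided after the group is known, and sections 5.2 and 6.1 together permit them. The opposite-direction argument is also only partial, because section 7.2 tests each outcome separately and any one comparison could still be shifted.

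**Conclusion.** The point holds in a limited form. For the in-lab studies, the plan describes pseudo-random assignment steered towards balance on age and sex, with unblinded staff and no stated concealment, in wording that differs from the other three sections. It permits intake-based exclusion and replacement with the group known. The next assignment may also be predictable, depending on the unstated algorithm. Selection bias therefore cannot be ruled out, but nothing in the documents shows that it occurs.

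The intake route follows from the text alone and needs no assumption. The guess rates of 67% to 86% rest on the illustrative settings above and describe how exposed an unconcealed rule would be, not what this trial does. The documents give no exclusion rate and no measure of how selection would relate to performance, so no bias estimate is offered. The concern goes beyond reporting because the order of reveal and eligibility decision would change, not only its description.

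**What to change.** In section 6.2, replace the pseudo-random rule and the requirement that the groups not differ with text along these lines:

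> Before each in-lab experiment opens, a computer-generated 1:1 list will be made, stratified by sex and age band, in permuted blocks of random size. It will be concealed from staff who recruit participants and run sessions. A participant's group will be revealed only after consent, completion of the intake questionnaires and recorded confirmation of eligibility. A replacement participant takes the next unused entry in the relevant stratum.

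The list could be held in Qualtrics, which is already used for consent and intake. State the age bands and who generates the list. Give sections 4 and 6.1 the same order of events, amend section 5.2 so that intake-based exclusion is decided before the reveal, and use the same description of assignment in section 7.1. If a concealed list already exists, the change is mostly a matter of saying so and fixing the order.

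The cost is a paragraph, matching edits in four sections and a one-time list for each experiment. Balance on age and sex becomes approximate rather than forced. For example, with four strata and blocks no larger than 4, an unfinished block leaves a stratum at most 2 apart, so the groups could differ by at most 4 × 2 = 8 (44 against 36 out of 80). Section 7.1 should allow for this. The change does not address losses after the reveal through withdrawal or incomplete data (sections 6.5 and 7.7); those should be reported by group.

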5.2 Number of Participants

Approximately five-hundred participants will be enrolled in the experiments. We plan to run between two and four behavioral studies ($N = 46-138$ each, depending on the exact parameters of the study) and one fMRI study ($N = 100$). These numbers were determined based on power analyses from past studies of statistical learning and episodic encoding (Sherman & [name] 2020) and acute stress effects on memory ([name] et al 2019).

Participants who do not meet our eligibility criteria as confirmed during recruitment (i.e., self-reporting that they are out of the age range or ineligible for MRI studies) will not be included in the participant count. For each participant who is excluded after their participation (i.e., due to responses on an intake questionnaire), we will recruit an additional participant so that the total number of usable participants matched the above-stated desired N s.

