6.1.1 Data Collection

Questionnaire and demographic data will be collected using Yale's HIPAA-aligned instantiation of Qualtrics. Please see section 4 (*Intake Procedures*) for a list of the validated questionnaires that will be used. Licensure/training is not required for the administration of these questionnaires.

Behavioral responses will be made on a computer and responses will be recorded with custom experiment programming software designed through Matlab's Psychtoolbox (Brainard, 1997) or Python's Psychopy (Peirce, 2007), programs widely used in psychological research. MRI data will be acquired on the Siemens's 3T Prisma Scanner at the BIC or BrainWorks. Data for online studies will be completed on participants' personal computers, and will be accessed through the Prolific or mTurk interface. Responses will be recorded with custom experiment programming software designed through Javascript.

All data will be coded in a de-identified manner and stored in password-protected computer files accessible only to the research team. fMRI data will be stored on the secured and HIPAA-aligned Milgram computer cluster managed and certified for compliance by the Yale Center for Research Computing. Backups of the fMRI data may be burned to DVDs at the scanner and locked in a cabinet in the [name] lab space. Behavioral data (e.g., button presses, verbal reports, eye-tracking images) will either be recorded on computers secured in the control room and transferred on an encrypted and passcode-protected flash drive to computers in the [name] lab or on a password-protected laptop computer with full disk encryption, which will otherwise be kept locked in the [name] lab space. All video data collected during the behavioral task will be discarded without being looked at within seven days of a participant's participation.

Correspondence with study participants and a spreadsheet linking participant ID codes with identifiable information will be kept on a password-protected desktop computer with full disk encryption in the locked research coordinator office in the [name] lab space. Paper consent forms will be stored separately from any data and in a locked cabinet in the [name] lab space. Electronic consent forms and demographic forms will be stored on the secure Yale Qualtrics server, a HIPAA-aligned tool for survey data collection.

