6.5 Withdrawal Procedures

Participants who withdraw from the study before completion will be given the opportunity to ask questions about the study. The data collected from these participants will not be analyzed.

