7.7 Handling of Missing Data

All data will be collected and stored electronically. Data will be missing only in the case of a technological failure (e.g., a computer error). Participants with incomplete datasets will be excluded from the analyses and replaced.

8 Data/Specimen Handling and Record Keeping

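### Section 6.2 rules out all blinding for a reason that covers only the water bath, so later exclusion and segmentation decisions may be made with group known

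*Combined protocol and SAP*

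**What the plan says.** Section 6.2 deals with masking in one sentence: "There will be no blinding procedures, as both the experimenter and participant will be aware of whether they are receiving the cold or warm water". The only reason given is that these two people know the water temperature. No other section masks any role. Section 8.2 (Data Quality Assurance) relies on training, a standard operating procedure and practice trials. The coding of data in 6.1.1 and 8.3 hides who a participant is, not which group they were in.

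Decisions that come after the bath appear in several places:

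- Section 5.2: "For each participant who is excluded after their participation (i.e., due to responses on an intake questionnaire), we will recruit an additional participant".
- Section 7.7: "Participants with incomplete datasets will be excluded from the analyses and replaced". The section expects data to be missing only through technical failure.
- Section 5.3 lists the eligibility criteria. Several need some judgement, such as whether a medical condition is significant or whether a drug affects the physiological stress response.
- Section 4 (fMRI Scanning) includes a T2 scan for hippocampal segmentation. Section 4.2.1 makes connectivity between hippocampal subregions, and between CA1 and entorhinal cortex, the focus of the neural aim.

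On the behavioural side, section 6.1.1 says that "responses will be recorded with custom experiment programming software".

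**The concern.** The bath cannot be masked, and nobody would ask for that. But the reason in 6.2 stops at the bath, while the rule it supports has no limit. Someone who later judges whether an intake answer makes a participant ineligible, whether a dataset is too incomplete to use, or where a subregion boundary lies does not need to know the group.

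The hypotheses in section 3.2 are directional: statistical learning up under stress, episodic encoding down. Anyone who knows the group also knows which results would support the hypotheses. If outcome data are also visible, borderline exclusions can shift the group comparison without any intent to do so. With the bath necessarily open, masking these later steps is the protection still available, and as written 6.2 gives it up by default.

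**Working it through.** **Text check.** For each later step, I asked whether the reason in 6.2 reaches it and whether another section masks it.

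- *Exclusion on intake answers (5.2, 5.3).* Under 6.1 the questionnaires are completed before the first saliva sample and the bath, so their content cannot depend on the bath. The decision, however, may be taken after participation, when group is known. Not reached by the reason; not masked.
- *Exclusion of incomplete datasets (7.7).* Completeness is not defined. Not reached; not masked.
- *Hippocampal segmentation (4).* The protocol does not say whether it is manual or automated. If any of it is manual, it is not reached and not masked.
- *Key presses and reaction times (6.1.1, 7.2).* Recorded by software, so there is little room for judgement in the score itself.
- *Online studies (4, 6.1).* No stress or control assignment, so the question does not arise.

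**Illustration of size.** The plan has no figure here to reproduce, and it states no exclusion rate. From section 7.1, n = 46 per condition. Everything else is assumed: an outcome with SD 1; k people in one arm, each m SD below the arm mean, excluded because of their result; replacements who on average score at the arm mean.

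Shift in the arm mean = k × m / 46, because the plan replaces those excluded and the arm stays at 46.

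- k = 2, m = 2: 4/46 = 0.087 SD.
- k = 4, m = 1.5: 6/46 = 0.130 SD.

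Standard error of the group difference = √(2/46) = 0.209 SD. The shifts are about 0.4 and 0.6 of it. Without replacement the divisor would be 46 − k, giving 4/44 = 0.091 and 6/42 = 0.143 SD, but that is not what the plan does.

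**Effect on type I error.** This is a simulation under a true null with a two-sided t-test at 0.05, 40 or 46 per group and 40,000 runs per setting. A random share of participants in both arms is borderline. Under masking, all borderline cases are replaced. In the unmasked worst case, a borderline case is replaced only when its result goes against the hypothesis.

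| Borderline share (assumed) | Type I error, worst case | Spurious difference |
|---|---|---|
| 5% | 5.2–5.5% | 0.04 SD |
| 10% | 6.6–6.8% | 0.08 SD |
| 20% | 10.9–12.1% | 0.16 SD |

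With masked decisions the error stayed between 4.7% and 5.2%.

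**The case against.** The strongest reply is that the documented room for discretion is narrow. Section 5.2 ties exclusion after participation to intake answers given before the bath. Section 7.7 expects only technical failures. No section allows exclusion for poor performance or as an outlier. All of this stands. It limits the likely size of the problem, but some criteria in 5.3 still need judgement and nothing prevents that judgement from being made with group known.

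A reader might infer more from the blanket sentence than the documents support:

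- *That scan quality control is planned without masking.* The protocol describes no scan quality control step or criterion. It can be covered in the fix, but not cited as a planned step.
- *That behavioural scoring is open to bias.* The analyses in 7.2 use reaction time, category-pair discrimination and exemplar recognition. Section 4 (Memory Tasks) has responses made by key or button. Recall is only a possibility there, and verbal reports appear once, in a list of stored data types in 6.1.1.
- *That the saliva assay is exposed.* Under 8.3 the samples carry no identifying information, and they are assayed for concentrations.
- *That the plan lets people be dropped for their scores, or that bias would favour the hypotheses throughout.* The illustration assumes outcome-driven exclusion in one arm, which no stated rule permits. Excluding a person also affects both outcomes: dropping people from the Stress arm who do poorly on both tasks would help the statistical-learning hypothesis and work against the episodic one.
- *That masking costs nothing.* Under 6.1 research staff both give the intervention and collect the data, so a person who ran the session may recognise an ID.

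**Conclusion.** The point holds in a limited form. The reason in 6.2 justifies an open water bath. It does not justify open decisions about exclusion and replacement or about any manual segmentation, and these may be made with group, and possibly outcome, known. Exclusion with replacement is the firmest ground, because the plan provides for it after participation. Segmentation is next, and depends on how much of it is manual.

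The size of any bias cannot be derived from the documents. The 0.09 to 0.13 SD shift (0.4 to 0.6 standard errors) and the worst-case type I error of about 5% to 12% rest on assumed exclusions driven by outcome; the upper end needs one participant in five to be borderline. They show what masking guards against and do not predict what will happen. The sentence should be changed, but the design is not undermined, because the main behavioural measures are machine-recorded.

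**What to change.** Replace the sentence in 6.2 with:

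> Participants and the experimenter giving the arm bath are not blinded. In the in-lab and fMRI studies, eligibility and incomplete-data exclusions are decided on coded participant IDs with the group and outcome variables withheld. Any manual segmentation, image-quality rating or recall scoring is done on coded IDs with group and all other outcome data withheld. The exclusion list is locked before group is merged.

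Because excluded participants are replaced during recruitment, each decision should be logged as it is made, and whoever holds the group key should arrange the replacement.

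The cost is small: coded IDs already exist under 6.1.1, so what is added is a separate key file, a locked list and one more data-handling step. Masking will be imperfect where someone who ran a session recognises the ID. Using a person who did not run that session would help, at some cost in staff time. Masking also does not replace written exclusion criteria. Nor does it address participants who withdraw, for whom section 6.5 says "The data collected from these participants will not be analyzed".
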